9.7.1 Primary Efficacy Endpoints - Anatomical Characteristics

The first primary efficacy endpoint will be the change from baseline in total LV EBD scores (UEUS vs. CEUS). Total LV EBD score is calculated as the sum of the individual scores (0, 1, or 2) assigned to each of the 17 segment images with a total score range 0-34.

The co-primary endpoint will be the proportion of subjects with adequate LV opacification. Left ventricular opacification will be graded as 0 to +3, 4-point rating scale. Left ventricular opacification rating of +2 (non-homogeneous) or +3 (complete and homogeneous) will be considered as adequate LV opacification.

9.7.2 Analysis Methods

9.7.2.1 Analysis of LV EBD Score

The null hypothesis of the primary test is that there is no difference between the CEUS and UEUS in the mean total LV EBD score in the pediatric population. The alternative hypothesis is that the CEUS is superior to UEUS in term of the mean total LV EBD score in pediatric population.

$H_0: \mu_{CE} - \mu_{UE} = 0$

$H_1: \mu_{CE} - \mu_{UE} > 0$

where μ_{UE} represents the mean of the total LV EBD score for the UEUS; and μ_{CE} represents the mean of the total LV EBD score for the CEUS.

For each blinded reader assessment, paired t-test will be used to compare total LV EBD score between the CEUS and UEUS. In addition, the 2-sided 95% confidence intervals (CIs) will be calculated for the mean total LV EBD scores for each exam as well as for the change from baseline (UEUS to CEUS). The distribution of the individual scores (0, 1, or 2) assigned to each of the 17 ventricle segments will be presented.

The study will be considered as a success for the primary efficacy endpoint if: 2 of the 3 readers achieve superiority of the CEUS over the UEUS in terms of the mean total LV EBD score. The satisfaction of superiority is met if the alternative hypothesis is concluded, i.e., $\mu_{CE} - \mu_{UE} > 0$ based on paired t-test at significance level of 0.05.

Inter-reader agreement of the assessment for each segment among 3 off-site readers will be evaluated (for UEUS and CEUS separately) by kappa statistic.

The number and percentage of subjects with reduction of inadequate LV EBD in at least one pair of adjacent segments (combined 4-chamber, 2-chamber, and 3-chamber view) following administration of IP will be summarized for each reader.

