9.7 Efficacy Analysis

The primary analysis will be based on the off-site reader evaluations. The analysis will be performed and presented separately for each reader. There will be no adjustment for multiple readers. There will be 2 primary endpoints for the study: the change from baseline (UEUS to CEUS) in total LV EBD score and proportion of subjects with adequate LV opacification. As we have to achieve success for both endpoints there will be no multiplicity adjustment for the analysis and power consideration.

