9.8 Sample Size

Sample size determination for this study was based on the 2-tailed paired t-test using software nQuery Advisor 7.0. The primary objective of this trial is to show a significant intra-subject change in total of LV EBD scores for each subject (Hypothesis specified above) from UEUS to LUMASON -enhanced echocardiography. Sample size determination for this study was based on the 2-tailed paired t-test.

A peer-reviewed publication showed ³⁷ that the percentage of endocardial border visualization at unenhanced harmonic images (74%) was significantly lower comparing to a contrast enhanced images (88%) in the suboptimal subjects non-diagnostic imaging group, which translated to the difference of 4 in total LV EBD scores. A previously conducted Bracco-sponsored study [REDACTED] had the same endpoint of the total LV EBD score range 0-32 assessed on harmonic

images on adult subjects with known or suspected coronary artery disease. The results from the analysis of the suboptimal subjects in this study showed that the average difference of the total LV EBD score between CEUS and UEUS was 3.2; the standard deviation of the difference was 8.3. Based on these results as the assumptions for current study and considering the probability of a Type I error (α) of 0.05 and the probability of a Type II error (β) of 0.10, 73 subjects will be needed to show a difference between CEUS and UEUS for 90% of power.

When the sample size is 73, a 2-sided 95% CI for a single proportion using the large sample normal approximation will extend 9% from the observed proportion for an expected proportion of 80% subjects with adequate LV opacification score. This can be translated as lower limit of 95% CI >70% for the observed proportion of subjects with adequate LV opacification score.

Based on the above considerations, for both endpoints (Total LV EBD score and LV opacification score), total of 73 evaluable subjects are needed. Considering 20% of early dropout, 92 subjects will need to be enrolled.

A subset of 12 subjects is considered to be sufficient for the estimation of the pharmacokinetic parameters, based on the findings of a prior study in healthy subjects.

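### Does the unlabelled 0.05 level in the EBD success rule leave the primary test open to a one-sided 5% reading?

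*Combined protocol and SAP*

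**What the plan says.** All of this is in the Combined protocol and SAP.

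- **Hypothesis (9.7.2.1).** The null is no difference in mean total LV EBD score. The alternative is directional: "The alternative hypothesis is that the CEUS is superior to UEUS in term of the mean total LV EBD score in pediatric population".
- **Test (9.7.2.1).** "For each blinded reader assessment, paired t-test will be used to compare total LV EBD score between the CEUS and UEUS". The number of tails is not given.
- **Success rule (9.7.2.1).** The endpoint succeeds if "2 of the 3 readers achieve superiority of the CEUS over the UEUS in terms of the mean total LV EBD score", with superiority judged "based on paired t-test at significance level of 0.05".
- **Interval (9.7.2.1).** "In addition, the 2-sided 95% confidence intervals (CIs) will be calculated for the mean total LV EBD scores for each exam". The same sentence extends the interval to the change from baseline.
- **Sizing (9.8).** "Sample size determination for this study was based on the 2-tailed paired t-test using software nQuery Advisor 7.0". The section repeats that the test is 2-tailed, refers back to the hypothesis already specified, and takes a type I error of 0.05, a type II error of 0.10, a mean difference of 3.2 and an SD of 8.3. It concludes that "73 subjects will be needed to show a difference between CEUS and UEUS for 90% of power".

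**The concern.** A directional alternative accepted at an unqualified 0.05 can be taken as a one-sided 5% test. That would put 5% in the superiority direction, against 2.5% for the 2-tailed test used in sizing. Neither passage that points to two sides is itself the decision rule: 9.8 describes how the number was obtained, and the 2-sided interval in 9.7.2.1 is introduced as an addition to the test. The opacification rule in 9.7.2.2, by contrast, is written directly on the lower limit of its 95% interval, so it raises no such question.

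What would be at stake is the pass/fail line for one of two endpoints that must both succeed. A reader whose result fell between the two cut-offs would pass under one reading and fail under the other. Under the one-sided reading, superiority could be declared for a reader whose reported 95% interval includes zero. A choice left open until results are known could be made to suit them.

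**Working it through.** **Inputs.** From 9.8: mean difference δ = 3.2, SD = 8.3, n = 73, α = 0.05, power 90%. From 9.7.2.1: success in 2 of 3 readers. The documents give no correlation between readers, so it is taken over the whole range from 0 to 1 in an equicorrelated normal model.

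**Step 1: which test gives 73?** Power of a paired t-test comes from the noncentral t distribution with n − 1 degrees of freedom and noncentrality (δ/SD)√n. At n = 73 the noncentrality is (3.2/8.3) × √73 = 3.294.

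| Test | Critical t (72 df) | Power at n = 73 | Smallest n for 90% |
|---|---|---|---|
| Two-sided 0.05 | 1.993 | 90.1% | 73 |
| One-sided 0.05 | 1.666 | 94.7% | 59 |

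At n = 72 the two-sided test has 89.7% power, so 73 is exactly the two-sided answer. The one-sided test does not reproduce it.

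**Step 2: where do the readings disagree?** The standard error is 8.3/√73 = 0.971. The smallest mean change that wins for a reader is

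- one-sided: 1.666 × 0.971 = 1.62 points;
- two-sided: 1.993 × 0.971 = 1.94 points.

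Example: an observed change of 1.8 gives t = 1.8/0.971 = 1.853. The one-sided p is 0.034 and the two-sided p is 0.068. The 95% interval is 1.8 ± 1.94, or −0.14 to 3.74.

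**Step 3: how often would one reader land in the gap?** This is the difference in rejection probability between the two tests.

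- No effect: 0.050 − 0.025 = 0.025.
- True change 1.8: 0.576 − 0.448 = 0.128.
- True change 3.2: 0.947 − 0.901 = 0.046.

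**Step 4: how often would the 2-of-3 verdict differ?** With independent readers, each with success probability p, the rule succeeds with probability 3p²(1 − p) + p³. With correlation 1 it succeeds with probability p.

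| True change | Correlation | One-sided reading | Two-sided reading | Difference |
|---|---|---|---|---|
| 0 | 0 | 0.0072 | 0.0018 | 0.005 |
| 0 | 0.5 | 0.027 | 0.011 | 0.016 |
| 0 | 1 | 0.050 | 0.025 | 0.025 |
| 3.2 | 0 | 0.992 | 0.973 | 0.019 |
| 3.2 | 1 | 0.947 | 0.901 | 0.046 |

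At a true change of 1.8, which lies inside the gap and is just over half the planned effect, the difference is about 13% (correlation 1) to 19% (correlation 0).

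**Step 5: do the plan's stated properties survive?** The EBD false-success rate peaks at 5.0% under the one-sided reading and 2.5% under the two-sided one. Section 9.7 requires both endpoints to succeed, which can only lower the trial-level rate. Per-reader power at the planned effect is 94.7% or 90.1%, so the 90% claim holds either way.

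**The case for a change.** The strongest case for acting is that this threshold decides a primary endpoint, that the success sentence cites neither 9.8 nor the confidence interval, and that two analysts could in good faith reach different verdicts on the same data. The false-superiority rate per reader doubles between the readings. One sentence would close the question at no cost in sample size. Nor can the SAP be relied on to settle it: Section 9 mentions one for recording changes in methodology and 9.9 for data handling, but no separate SAP text is in the supplied document, so whether it states the tails could not be checked.

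Some of this stands. The label is absent from the success sentence, and a result between 1.62 and 1.94 points would be awkward to report.

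The claim that 9.7.2.1 prescribes a one-sided 5% test does not stand. It gives a level and no tails, and a superiority conclusion drawn from a two-sided 0.05 test with the effect in the favourable direction fits the wording equally well. Sections 9.7.2.1 and 9.8 name the same test and the same level, and 9.8 refers back to the same hypothesis; only 9.8 states the tails, and it does so twice. No passage mentions a one-sided test. The direction of the alternative is the only support for that reading.

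**Conclusion.** No change follows. The EBD success rule omits a word that the plan's sizing, its interval for the change and its arithmetic all supply. An analyst following the documents would run the two-sided test at 0.05 and require the change to favour the enhanced examination, which is the same as requiring the lower limit of the 2-sided 95% interval for the change to exceed zero. Stating this would record the evident rule without correcting any number or result: 73 evaluable subjects, 92 enrolled and 90% power all stand.

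The room for dispute is a band of about 0.32 points (1.94 − 1.62) in a reader's mean change. It alters the 2-of-3 verdict with probability about 0.5% to 2.5% under no effect and about 1.9% to 4.6% at the planned effect. It matters more, about 13% to 19%, only if the true change is near 1.8. Even under the less strict reading, false success on this endpoint does not exceed 5%.

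The cut-offs assume 73 evaluable subjects and an observed SD of 8.3. The 2-of-3 figures assume equally correlated normal reader statistics with a common effect, over correlations from 0 to 1.

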5.4.1 Inclusion Criteria

Enroll a subject in the study if they meet the following inclusion criteria:

- Is male or female, 9 to 17 years of age;
- Written informed consent is obtained from the subject's parent(s) or legal acceptable representative(s) (according to local regulations);
- Assent from the subject is obtained when applicable, that is, when it is required according to local regulations (IRB requirements) (see section 10.2);
- Is suspected of having cardiac disease or undergoing evaluation of cardiac anatomy for congenital heart disease;
- Has undergone a previous transthoracic echocardiogram within a one month period prior to enrollment in this study resulting in suboptimal LV EBD defined as ≥ 2 contiguous segments in any given view that cannot be visualized.

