7.7 Efficacy Evaluations

For all subjects, UEUS and CEUS images will be randomized and independently evaluated off-site by 3 blinded readers unaffiliated with the enrollment centers. No on-site evaluation of efficacy will be performed for this study.

From the apical 4-chamber, apical 2-chamber and apical long (3-chamber) views, the heart will be divided into 17 segments according to the guidelines of the American Society of Echocardiography¹⁷ as seen in Figure 1.

Figure 1 Three echocardiographic apical views used in the study

EBD for each segment will be graded by each off-site reader as:

- 0 = Inadequate (endocardial border not visible)
- +1 = Sufficient (endocardial border barely visible)
- +2 = Good (endocardial border clearly visible).

A separate off-site methodology document will be prepared and will contain the details regarding how the images will be anonymized, randomized and presented to the readers. No clinical information will be provided to the readers.

Both the UEUS and CEUS examinations must be identified by subject study identification number and stored as DICOM clips for transfer to the central imaging lab according to the instructions provided. Under Good Clinical Practices guidelines, the investigational sites are also required to maintain the subject's examination as a record of the study.

The timing of LV EBD assessment should start when LUMASON reaches from the apex to the mitral valve plane level.

The degree of LV opacification following injection will be graded according to the following 4-point rating scale:

- 0 = none, i.e., no visible contrast within the left ventricular cavity
- +1 = faint, i.e., weak or trace effect of contrast within the left ventricle
- +2 = non-homogeneous, i.e., some areas of the left ventricle fully opacified but without a time when the whole cavity is filled with contrast to the same high intensity
- +3 = complete, homogeneous and high intensity effect.

Useful appearance of contrast within the left ventricle including ventricular opacification rating of +2 (non-homogeneous) or +3 (complete and homogeneous) will be considered as adequate LV opacification.

8 Reporting Safety Information

The Investigator is responsible for the detection, documentation and reporting of adverse events.

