9.2 Analysis Population

Safety Analysis Population – all subjects who received IP will be included in the safety analysis population.

Efficacy Analysis Population – all subjects who received IP and have data available for both non-contrast echo exam and contrast echo exam will be included in modified Intent-to-Diagnose population (ITD population).

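### The descriptive adjacent-pair percentage counts improvement only; printing the worsening count and a paired 2x2 beside it is a cheap improvement

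*Combined protocol and SAP*

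**What the plan says.** Section 9.7.2.1 plans, per reader and with the three apical views combined, "The number and percentage of subjects with reduction of inadequate LV EBD in at least one pair of adjacent segments" following the injection. It does not say what change in a pair counts as a reduction, or whether a pair must lie within one view. It plans no count of subjects who move the other way.

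The same section plans other per-reader outputs: a paired t-test on the total score, two-sided 95% CIs for each exam and for the change, and the distribution of 0/1/2 scores in each of the 17 segments. It also states that "Inter-reader agreement of the assessment for each segment among 3 off-site readers will be evaluated" by kappa, which is agreement between readers, not of a reader with himself or herself.

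The efficacy population in section 9.2 is "all subjects who received IP and have data available for both non-contrast echo exam and contrast echo exam". Section 7.7 says that "UEUS and CEUS images will be randomized and independently evaluated off-site by 3 blinded readers", and a score of 0 means that the border cannot be seen. Section 5.4.1 admits a subject on an earlier echocardiogram with at least 2 "contiguous segments in any given view that cannot be visualized".

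**The concern.** Each subject has many adjacent pairs, and one improving pair is enough to be counted, even if other pairs stay or become inadequate. Two readings of similar images will differ in some segments. Without a contrast effect those differences go up and down equally often, but only the upward ones are tabulated.

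The plan's own figures suggest that downward movement will be common. Section 9.8 takes from an adult study a mean change that "was 3.2; the standard deviation of the difference was 8.3". If changes are roughly normal (an assumption), the share of subjects scoring lower with contrast is Φ(-3.2/8.3) = Φ(-0.386), or about 35%. That concerns the total score, not pairs, but shows that a one-way count would leave out a real part of the picture.

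At stake is how one supportive table is read. A counted subject may still meet the entry definition at CEUS, and the table would not show it.

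**Working it through.** **1. The plan's own figure.** A two-sided paired t-test at 0.05 with difference 3.2 and SD 8.3 has 90.1% power at n = 73. Allowing for dropout, 73/(1 - 0.20) = 91.25, rounded up to 92. Both figures reproduce, and nothing below changes them.

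**2. What the planned outputs show.**

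- The t-test and CI give the net mean change.
- The segment distributions give the share scored 0 at each exam. They are not cross-tabulated within subject.
- Kappa compares readers.
- The adjacent-pair count gives subjects improving.
- No output gives subjects worsening.

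**3. Illustration with no contrast effect.** Two exchangeable readings per subject were simulated from a latent-normal model with 17 segments scored 0/1/2 and 60,000 subjects per setting.

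- From the documents: 26% of segments scored 0, being 100% minus the visualization rate in section 9.8 ("the percentage of endocardial border visualization at unenhanced harmonic images (74%) was significantly lower").
- Assumed: the amount of reading noise and the adjacency map (three separate chains of segments; Figure 1 is not shown).
- Kappa here is for score 0 against visible. For example, with 91.8% agreement, chance agreement is 0.26² + 0.74² = 0.615, and (0.918 - 0.615)/(1 - 0.615) = 0.79.
- Loose rule: a pair is both 0 at UEUS and no longer both 0 at CEUS. Strict rule: both segments of such a pair become visible.
- The last column is the 2x2 on having any both-0 pair.

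| Same-reader kappa | SD of total change | Loose: improved / worsened | Strict: improved / worsened | Converted / reversed |
|---|---|---|---|---|
| 0.79 | 1.7 | 23.5% / 23.7% | 2.9% / 3.0% | 5.1% / 5.2% |
| 0.70 | 2.1 | 29.1% / 29.2% | 5.6% / 5.6% | 6.5% / 6.4% |
| 0.57 | 2.5 | 35.6% / 35.6% | 10.1% / 10.2% | 8.7% / 8.8% |
| 0.39 | 3.2 | 42.2% / 42.1% | 18.3% / 18.1% | 11.9% / 11.8% |
| 0.47 (noise partly shared across the exam) | 6.0 | 35.0% / 34.9% | 16.7% / 16.5% | 13.0% / 12.8% |
| 0.31 (noise partly shared across the exam) | 8.2 | 38.4% / 38.2% | 23.4% / 23.2% | 16.8% / 16.8% |

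Other layouts and noise settings widen the range. At kappa 0.73-0.83 the loose rule gives 17-24% and the strict rule 1-3%. With noise large enough to produce an SD near 8.3 by itself, kappa is about 0.20-0.42, and the rules give 30-43% and 17-26%. Overall that is about 17-43% loose and 1-26% strict. If 40% of segments were scored 0 instead of 26%, the figures would be higher: 33-63% loose and 4-31% strict.

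**4. What the 2x2 adds.** In every row the two directions match, so the net change is about zero, as it should be with no effect. The conversion percentage among subjects with a pair at UEUS is not zero. In the first row, 39.4% of subjects have a pair at both exams, giving 5.1/(39.4 + 5.1) = 11%. In the last row, 28.3% do, giving 16.8/(28.3 + 16.8) = 37%. It therefore has to be shown with the reversals.

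**5. How it would read at n = 73.** Net change is (b - c)/n, with standard error √[b + c - (b - c)²/n]/n.

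- b = 9 converted, c = 9 reversed: net 0, 95% CI -11.4 to +11.4 points.
- b = 25, c = 9: net 16/73 = 21.9 points; standard error √(34 - 256/73)/73 = 0.0756; 95% CI 7.1 to 36.7 points.

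The converted count alone would not distinguish 25 against 9 from 25 against 25.

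**The case against.** A reader might infer that the plan cannot tell contrast benefit from reading variability. The documents do not support that. Symmetric noise leaves the mean change at zero and the share of segments scored 0 unchanged, and section 9.7.2.1 reports both for each reader. Only the subject-level count by direction is missing.

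A reader might also infer that the percentage would be large and nearly uninformative. That needs most of the SD of 8.3 to be reading error, which implies same-reader kappa of about 0.2-0.4. Section 9.8 gives no such split, and the SD may also hold real differences in benefit between patients. In simulations where it is mainly varying benefit and kappa is about 0.9, the loose count does separate: 12-23% with no effect against 28-54% with a 3.2-point gain. Where it is mainly shared noise, the figures are 31-43% against 36-48%. The documents do not settle which holds.

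Two further objections have force. Independent evaluation in section 7.7 may mean only that the readers do not confer; how the two exams are presented is left to a separate methodology document. Closer pairing of the reads could reduce the noise but would not make the count two-directional. Section 9.9 also leaves data handling to the SAP, which might define the pair rule; the available text does not.

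The Introduction cites 75% to 90% of suboptimal studies made diagnostic by contrast, but the plan does not call its own count conversion. A 2x2 figure approaches that scale only if expressed among subjects with an inadequate pair at UEUS, and having no such pair is not the same as a diagnostic study.

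What stands is narrow: the count runs one way, its rule is undefined, and the opposite count is not planned.

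**Conclusion.** The point holds as a minor improvement to a descriptive table. The planned count is above zero without any contrast effect unless repeat readings agree perfectly, and it does not show how many subjects moved each way. It plays no part in the total-score test, the opacification criterion, the two-of-three-reader rule or the 73/92 sample size.

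The size cannot be fixed from the documents. The ranges of about 17-43% (loose rule) and 1-26% (strict rule) rest on an assumed latent-normal model, an assumed adjacency layout, 26% of segments scored 0, and a range of repeatability that nothing in the plan confirms. The pair rule matters as much as the noise: at kappa 0.70 the same readings give 29% under one rule and 6% under the other.

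**What to change.** In section 9.7.2.1 or the SAP, before the reads are analysed:

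1. State the pair rule (no longer both 0, or both visible), the adjacency (within view or pooled over views) and the denominator.
2. Print beside the count, for each reader, the mirror count of subjects with a newly inadequate pair under the same rule.
3. Add a per-reader paired 2x2 in the section 9.2 efficacy population: any adjacent same-view pair with both segments scored 0, UEUS yes/no by CEUS yes/no. Report both discordant counts, the net change with 95% CI, and the conversion percentage among subjects with such a pair at UEUS.
4. Keep all of this descriptive, with no success role. McNemar's test is optional: in the shared-noise simulations with a 3.2-point gain, its power at n = 73 is only about 40-59%.

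The cost is one extra table per reader, from scores already collected. The supportive percentage may look less favourable once worsening is shown beside it.
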